4.6 COMPENSATION

Participants will receive the equivalent of US \$8 in goods or cash for the screening visit, as this will require the collection of blood for laboratory testing. Participants will receive \$15 in goods or cash for their participation in baseline. Participants will receive the equivalent of US \$8 in goods or cash for the short check-in visits at weeks 1 and 7, the equivalent of US \$12 in goods or cash for 2-, 4- and 6-week visits, and the equivalent of \$23 in goods or cash for 8- and 12-week visits, which will require the collection of blood for laboratory testing (8-week only) and cold pressor testing.

4.7 RETENTION

Baseline visit: Retention begins at baseline by ensuring that the participant enjoys the experience of participating in the study, by explaining the informed consent and what would happen in the study, and by collecting excellent contact information, including both the address where the participant is registered and the address where the participant is currently staying. Participants will be asked to provide contact information for 4-5 alternative contacts who may know their whereabouts. Alternative contacts can include friends, family members, and social workers. Participants will be asked if any of their friends are participating in the study and to include them as alternative contacts, if possible. Contact numbers must be verified by calling the numbers with the participant present, using the following script:

I am calling from Pavlov University. Your friend/relative [NAME] is here with me and just enrolled in a study. He/she has listed you as an alternative contact. We will only call you if we are having trouble reaching [NAME] to see if you can help us connect with them. Today I am just calling to confirm that this number is active.

If the alternate contact cannot be reached at the baseline visit, the RA will try to reach the contact again at the next in-person study visit. If the RA is unable to reach the contact at the following study visit, the

participant will be asked to provide a different alternative contact. Participants will also be asked for their email address and membership to any social networking platforms.

All visits: Participants will be offered tea, coffee, water, and snacks at each study visit to make their experience in the research study more enjoyable.

RA will offer to help participants add the next scheduled study visit to the calendar in their phone and set a reminder in their phone.

Follow-up visits: Contact information for participant and alternatives will be reviewed and updated at every visit.

Other strategies: Participants will be contacted by telephone with appointment reminders and email, if one is provided. The study team will also utilize social networking to connect with participants. If participants are unable to be reached via phone, in addition to attempting to reach them via text messaging and email, participants will be sent private messages on Vkontakte (Russian social network) utilizing an existing standard script to remind them of their upcoming study visit. No sensitive information will be revealed or ascertained using this method. Study participants will be asked to contact the study team if their phone number changes between study visits; participants will be compensated 300 rubles in goods or currency for this information. All no-shows will be followed up to reschedule appointments.

Transportation will be arranged (i.e., a social taxi or Uber) for participants who are unable to come to First St. Petersburg Pavlov State Medical University due to a lack of available transportation.

5. ASSESSMENTS

5.1 BASELINE ASSESSMENT

Participants will be assessed as part of this study using validated interview instruments covering the following topics:

- Demographics (marital status, education, employment, individual Income/security, date of birth, spouse HIV status, living situation)
- Alcohol use by the Timeline Followback (TLFB) calendar method with a 30-day assessment^{4,5}
 - Participants will also be provided with a calendar to record daily alcohol use. They will be asked to complete this calendar at home and bring it back to all subsequent study visits.
 The calendar will be used as an aid by the RA when completing the TLFB with the participant.
- Alcohol Use Disorder using the AUDIT (baseline only).6
- Alcohol craving measured by the Penn Alcohol Craving Score⁷
- Depressive symptoms through the Center for Epidemiologic Studies Depression Scale (CES-D)⁸
- Anxiety by the Generalized Anxiety Disorder 7-item Scale (GAD-7)9
- ART use and adherence, using modified Adult AIDS Clinical Trial Group (AACTG) ART adherence questions¹⁰

- Co-morbidities by an adapted Veterans Aging Cohort Study patient questionnaire¹¹
- HIV symptoms through a validated HIV Symptom Index from the NIAID Adult AIDS Clinical Trials Group
- Prescription and non-prescription medication use
- Brief Pain Inventory using a modified Short Form of the Russian Brief Pain Inventory¹²
- Adjunct treatments of pain
- Drug use and HIV Risk Behaviors by an adapted version of the Risk Behavior Survey^{13,14}
 - o Participants will be asked about lifetime use and past 30 days use.
- General health, quality of life, and cognitive function by the Veterans RAND 12-Item Health Survey (VR-12) and the Medical Outcomes Study HIV Health Survey (MOS-HIV)^{15,16}

5.2 FOLLOW-UP ASSESSMENTS

Content of assessments administered at the 4-, 8-, and 12-week visits will be subsets of the baseline assessment. Please see table of study questionnaires at the end of this section. Sections not administered at baseline, but administered at follow-up visits include:

- Medication adherence using modified Adult AIDS Clinical Trial Group (AACTG) ART adherence questions¹⁰
- Medication satisfaction via the Treatment Satisfaction Questionnaire for Medication (TSQM)¹⁷
- Medication tolerability using modified Adult AIDS Clinical Trial Group (AACTG) ART adherence questions¹⁰

5.2.A. MEDICATION VISITS ASSESSMENTS

Medication adherence and symptoms will be assessed at weeks 1, 2, 6, and 7.

			Treatment				Post-	
								Treatment
Administered Assessment	Baseline	1-week	2-week	4-week	6-week	7-week	8-week	12-week
Demographics	X							
30-day Alcohol Timeline Followback (TLFB)	X			X			X	X
Alcohol Use Disorder (AUDIT)	X							
Alcohol Craving	X			X			X	X
Depressive Symptoms (CES-D)	X			X			X	X
Anxiety (GAD-7)	X			X			X	X
ART Use & Adherence (Adherence at baseline & 12-week only)	X			X			X	X
Co-Morbidities	X							

HIV Symptom Index	X							
HIV Risk Behaviors	X							
Medications	X			X			X	X
Brief Pain Inventory	X	X	X	X	X	X	X	X
Self Management of Pain	X							
Drug Use (modified RBS)	X			X			X	X
VR-12 Health Survey & MOS	X			X			X	X
HIV								
Baseline Symptom	X							
Monitoring								
Follow-Up Symptom		X	X	X	X	X	X	
Checklist								
Medication Adherence		X	X	X	X	X	X	
Medication Satisfaction			X	X	X		X	
(TSQM)								
Medication Tolerability		X	X	X	X	X	X	

6. PARTICIPANT SAFETY

Participant safety will be monitored every two weeks and more frequently, if necessary.

6.1. SPECIFICATION OF SAFETY PARAMETERS

An **Adverse Event (AE)** is defined as any untoward or unfavorable medical occurrence in a human subject, including any abnormal sign (for example, abnormal physical exam or laboratory finding), symptom, or disease, temporally associated with the subject's participation in the research, whether or not considered related to the subject's participation in the research.

An AE can therefore be any new sign, reaction, symptom, event, disease or a worsening in frequency or severity of a preexisting condition that occurs during the course of the study.

Stable chronic conditions that were present prior to study entry and do not worsen are not considered AEs.

SERIOUS Adverse Event (SAE) – for an event to be defined as serious, it will be Grade 1-6 below. Grade 0 would be "not serious".

Grade (1) results in death;

Grade (2) is life-threatening (places the subject at immediate risk of death from the event as it occurred);

Grade (3) results in inpatient hospitalization or prolongation of existing hospitalization;

Grade (4) results in a persistent or significant disability/incapacity;

Grade (5) results in a congenital anomaly/birth defect; or

Grade (6) based upon appropriate medical judgment, may jeopardize the subject's health and may require medical or surgical intervention to prevent one of the other outcomes listed in this definition (examples of such events include allergic bronchospasm requiring intensive treatment in the emergency room or at home, blood dyscrasias or convulsions that do not result in inpatient hospitalization, or the development of drug dependency or drug abuse).

Unanticipated Problem (UP) – for an event to be an Unanticipated Problem it must

- be unexpected AND
- be related or possibly related to participation in the research AND
- suggest that the research places subjects or others at a greater risk of harm (including physical, psychological, economic, or social harm) than was previously known or recognized. OR meet the definition of SERIOUS

Suspected Adverse Drug Reaction – Any adverse event for which there is a reasonable possibility that the drug caused the adverse event. Reasonable possibility means there is evidence to suspect a causal relationship. It is considered unexpected if it is not consistent with the risk information described in the general investigational plan. A suspected adverse drug reaction will be defined as a recorded adverse event that is unexpected and deemed to be possibly, probably, or definitely related to the study drug.

6.2 THE METHODS AND TIME FOR ASSESSING, RECORDING, AND ANALYZING SAFETY PARAMETERS

- Participant symptoms will be assessed at baseline to document any chronic conditions or symptoms that existed prior to introduction of study medication. These will be documented on the Baseline AE log. This list will be reviewed and compared to reported events throughout the study. If the participant reports the same ongoing symptom (same severity) during subsequent visits, the symptom should not be recorded as an Adverse Event (AE). If the event is new (not previously reported) or worsened, as determined by RA, then the AE should be reported.
- During each scheduled visit, the RA will ask the participant how he or she feels and review the list of symptoms of concern (starting with the symptoms recorded at the previous visit). Any event that meets the above criteria for an AE/SAE/UP must be recorded. In the case of unresolved AEs, clinical staff will update the AE log with any follow-up information that is gathered during their investigation.
- The site will receive the results of all blood work that is performed on study participants from the designated lab. If the lab results meet the criteria described in the protocol as an AE and are considered clinically significant by the site clinician then an AE will be recorded. **See**"Discontinuation of Medications" for severe hepatoxicity thresholds.
 - O Participants will be alerted of abnormal lab results and will receive a recommendation to see their local provider. All abnormal lab results obtained at the baseline visit will be listed on the Baseline AE log.

- All AEs will be assessed to determine if they meet criteria for a Serious Adverse Event (SAE). [name], MA, MPH and [name], MPH will be designated to distinguish a serious adverse event (SAE) from a non-serious adverse event. Drs. [name], PhD, D.Med Sci and [name]. PhD will monitor SAE and AE on site. If the AE is serious, then the SAE form must be completed and appropriate reporting measures followed (see below). Investigators are encouraged to consult with the US team, if they are uncertain how to classify an event.
- The list of subject's current medications will be reviewed and updated at every study visit, starting at baseline.

The study will take place in a medical setting where standard procedures are in place to assist patients who experience acute events. If consequences arise due to research procedures (e.g. distress, anxiety, suicidal thoughts,) the physician investigators will be available to assess participants and make appropriate interventions or referrals based on the clinical circumstances. Any participant who voices current suicidality, is experiencing a psychiatric emergency, or expresses the intent to harm others during the assessments will be reported to an on-site physician, immediately. That physician will determine the appropriate course of action, which will depend on location of the event and the clinical situation. Patients will be escorted to receive care by appropriate staff if deemed necessary.

- If an event is discovered outside of the scheduled study visits, it must still be recorded accordingly.
- Action Taken will be determined by the RAs for all AEs that are Mild and Moderate (unless specified below) and by [name] or [name] for SAEs and AEs that are severe, life-threatening or fatal.

6.3. PROCEDURES FOR ELICITING REPORTS OF AND FOR RECORDING AND REPORTING ADVERSE EVENT AND INTERCURRENT ILLNESSES

For any reported side effect: While with the participant, study personnel will listen, identify, and document the symptoms. The following symptoms will be assessed at baseline and during medication check-ins and study visits while participant is taking the study medication. All events will be documented on the Symptom Checklist and on AE forms.

Symptom
Agitation and/or Irritability
Anger
Depressed mood
Anxiety (includes nervousness and panic attacks)
Insomnia and/or other sleep problems
Abnormal dreams and/or nightmares
Headaches
Dizziness/lack of coordination
Nausea and/or vomiting
Joint/muscle pain
Abdominal pain/cramps

Fatigue
Drowsiness
Difficult speaking
Tremor
Jerky movements
Fever
Double vision
Swelling (legs or feet)
Unusual eye movement

6.3.A. OTHER EVENTS

- Other events may or may not be associated with study drug use, but will be recorded, AE form completed and [name] or [name] will be notified immediately to address the report.
- [name] or [name] will evaluate the reported symptoms using clinical judgment to determine if they are related to the study and if study medication should be adjusted or ceased.
- If [name] or [name] determine that study medications should be ceased, study personnel will attempt to contact the participant as soon as possible.
- If applicable, staff can advise participants to contact their physician immediately or call emergency services.
- Participants will receive a card to provide to medical staff in the case of a hospitalization or emergency stating that they are involved in a research study and are randomized to one of two study medications or placebo.

6.3.B. ADVERSE EVENT REPORTING

The following information should be present to complete AE and SAE forms during the initial report (on the day of finding out about the event):

- Description of the event
- Date of onset and resolution (if known)
- Severity based on established criteria:
 https://ctep.cancer.gov/protocoldevelopment/electronic_applications/docs/CTCAE_v5_Quick_Reference_5x7.pdf* See Box 1

Box 1. Guidelines for Severity Grades

- *Research assessor will refer to the guide for unique clinical descriptions of severity for each AE, which will follow the general guideline below:
- Grade 1 Mild; asymptomatic or mild symptoms; clinical or diagnostic observations only intervention not indicated.
- Grade 2 Moderate; minimal, local or noninvasive intervention indicated; limiting age-appropriate instrumental activities ADL*.
- Grade 3 Severe or medically significant but not immediately life-threatening; hospitalization or prolongation of hospitalization indicated; disabling; limiting self-care ADL**.
- Grade 4 Life-threatening consequences; urgent intervention indicated.
- Grade 5 Death related to AE.

Not all Grades are appropriate for all AEs. Therefore, some AEs are listed with fewer than five options for Grade selection. Grade 5 (Death) is not appropriate for some AEs and therefore is not an option.

Activities of Daily Living (ADL)

- *Instrumental ADL refer to preparing meals, shopping for groceries or clothes, using the telephone, managing money, etc.
- **Self care ADL refer to bathing, dressing and undressing, feeding self, using the toilet, taking medications, and not bedridden.

- Assessment of expectedness (is the event anticipated in terms of nature, severity, or frequency)
 given (a) the research procedures that are described in the IRB protocol and informed consent
 document; and (b) the characteristics of the subject population being studied
- Assessment of relatedness to study drug

· Any actions taken

Following the initial report, additional information may need to be gathered to complete the AE and SAE forms and to evaluate the event for relatedness. This process may include obtaining hospital discharge reports, physician records, autopsy records or any other type of records or information necessary to provide a complete and clear picture of the SAE and events preceding and following the event.

 All adverse events (including serious adverse events) will be followed until the event is resolved, stabilized, or until the end of individual's participation in the study. Study investigators and clinicians will determine a follow-up plan (i.e., frequency and type of follow-up) on a case-by-case basis based on their clinical judgment.

6.3.C. SAE REPORTING

If the SAE is not resolved or stabilized at this time or new information becomes available after the SAE form is completed, the SAE form should be updated as soon as possible. Any changes or updates to the SAE form will need to be re-reviewed and re-authorized by the study clinician.

In some cases, the study clinician may be unsure upon first learning of an SAE whether it is study related and/or expected, because study staff are awaiting more complete medical records. In such cases, the study clinician should make his/her best estimate of relatedness and expectedness, understanding that these determinations can be updated later. When updating determinations at a later date, the rationale for the change should be included in the SAE narrative.

SAEs and unanticipated events which are considered "at least possibly related" during the treatment and follow-up phases will be reported to the local IRB and to NIAAA within 48 hours of knowledge of the SAE and all other SAEs and unanticipated events will be reported within the time period mandated by the local IRB as indicated below.

The site must actively seek information about the SAE until the SAE is resolved, stabilized or until the participant is lost to follow-up and terminated from the study.

To summarize: upon determining an Adverse Event is Serious, the following procedures should be followed:

- The study staff, while meeting/talking with the participant or person providing details on the event, will gather as much information about the event from the participant as possible and complete the appropriate forms.
- The completed AE and SAE forms will be reviewed by key personnel on the Pavlov team (e.g. [name]
 or [name]). Any relevant clinical documents (labs, physician notes) available at that time will be
 provided to key personnel on the Pavlov team (e.g. [name] or [name]) within 24 hours of
 finding out about the event.
- After initial notification, the SAE must be updated with any additional information.

All unanticipated problems must be reported to the US team immediately.

AEs and SAEs will be reported to the URBAN ARCH Data Safety Monitoring Board every six months and as needed.

BUMC Reporting Guidelines:

Reporting to the Boston Medical Center and Boston University Medical Campus IRB

Information	Description	Form to use	When to Report
. Unanticipated Problem associated with a fatal or life- threatening event A fatal or life-threatening event that qualifies as an Unanticipated Problem (event was unexpected AND related/possibly related AND suggests greater risk, see definitions above)		Reportable Events and New Information AND	Within 2 days of the PI learning of a fatal or life-threatening event
		Change Request & Amendments addressing needed changes	As soon as practical
Unanticipated Problem NOT associated with a fatal or life- threatening event	An event that qualifies as an Unanticipated Problem (event was unexpected AND related/possibly related AND suggests greater risk, see definitions above) – whether or not it is also an Adverse Event or Serious Adverse Event	Reportable Events and New Information AND	Within 7 days of the PI learning of event
	Adverse Event or Serious Adverse Event	Change Request & Amendments addressing needed changes	As soon as practical
 Safety Monitors' Reports with recommended changes 	DSMB reports, Data Monitoring Committee reports, Adverse Event Monitoring Committee reports, audit reports, etc. with recommendations for changes to the study	Reportable Events and New Information AND	Within 7 days of the PI receiving the recommendations
		Change Request & Amendments addressing needed changes	As soon as practical
4. Major Deviations	A violation of IRB requirements or an unapproved change in the research study design or procedures that may affect the participant's rights, safety or well-being, that may affect the reliability of the study	Reportable Events and New Information	Within 7 days of the PI learning of the deviation

	data, or was the result of willful misconduct.		
5. Adverse Events that are NOT Unanticipated Problems	All Adverse Events and Serious Adverse Events (see definitions above) that do NOT qualify as an Unanticipated Problem (event was expected OR unrelated OR suggests no new risk).	Continuing Review Submission: Section 4 if a Data Safety Monitoring Board (DSMB) report Section 5 if no DSMB (AE/SAE summary report - must include Pl's conclusion that the pattern of events does not suggest a greater risk of harm)	At the time of Continuing Review
6. Safety Monitors' Reports without recommended changes	DSMB reports, Data Monitoring Committee reports, Adverse Event Monitoring Committee reports, audit reports etc. without recommended changes to the study	Attached to Continuing Review Submission Section 4 (The most recent report must be attached)	At the time of Continuing Review

Pavlov Reporting Guidelines:

What Event is Reported	When is Event Reported
	Within 7 calendar days of initial receipt of information
	Within 15 calendar days of initial receipt of information
AEs and UPs	On a quarterly basis

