Please note that these side effects were reported among people taking 50mg of naltrexone. This study will use low dose naltrexone (4.5mg) and side effects are expected to be milder. In order to help prevent these adverse effects, participants will be instructed not to take more medication than what is provided by the study. Study clinicians will also be monitoring for signs of naltrexone overdose. These adverse effects are not expected to be likely.

3.3.B. GABAPENTIN

Participants randomized to this group will receive gabapentin for 8 weeks.

Gabapentin dosing will start on the day of the baseline visit after successful passing of the naloxone challenge. If the participant does not pass the naloxone challenge, he/she will be brought back within a week to try again.

Participants will be instructed to take the medication from one to three times daily for 8 weeks. Medication will be packaged in pill boxes. Participants will receive 1 box of 7 capsules and 1 box of 21 capsules at baseline (14 days worth of medication), at the 1-week visit participants will receive 1 box of 42 capsules, at the 2-week visit participants will receive 2 boxes of 42 capsules, at the 4-week visit participants will receive 2 boxes of 42 capsules; at the 6-week visit participants will receive 1 box of 33 capsules.

Participants randomized to the gabapentin arm begin on a dose of 300 mg daily (300 mg qd). In week 2, participants will take 300 mg of gabapentin three times daily. In week 3 the dose will be titrated up to 1800 mg daily (300 mg+300 mg tid) will remain on the dose until week 8, when they will be tapered back down to 900 mg daily (300 mg tid). In week 8, in days 1-4 participants will take 1800 mg daily (300 mg+300 mg tid); in days 5-7, participants will take 900 mg daily (300 mg of gabapentin three times daily). Gabapentin will only be titrated up as tolerated by the participant. Participants will be monitored regularly for side effects and medication tolerability (weeks 1, 2, 4, 6, and 7) If a participant experiences adverse effects while on medication, the participant's dose will be reduced down to the previous dose (or to a lower dose that the participant can tolerate). Research Assessors in this study are all trained addiction psychiatrists, with experience in clinical trials and adverse event monitoring.

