Return all unused medication to the study site.

DATE OF MANUFACTURE:

SHELF LIFE:

3.4.D. LOST OR STOLEN STUDY MEDICATION

If participants report lost or stolen medication, they will be provided with extra study medication. If participants report losing medication more than once, the study team will be alerted and the case discussed to determine a plan of action.

3.4.E. DISCONTINUATION OF STUDY MEDICATION

If as a result of study testing at week 4, a participant is found to have AST/ALT >10x normal, medications will be discontinued and the participants will be appropriately monitored for resolution of the abnormalities. If a participant has AST/ALT >5x normal as a result of study testing at week 4, participant will be rechecked at their 6-week visit to ensure levels do not increase to the threshold of discontinuation. Any participant with symptoms of acute hepatic failure (jaundice, dark urine) will have AST/ALT checked.

Those who discontinue medication will be followed and analyzed by intention to treat.

Participants found to be pregnant during the study will have their study medication discontinued, but will still be followed-up for the duration of the study. Participants who report pregnancy outside of study

visits will be instructed to immediately discontinue their study medication and requested to come in for a confirmatory urine pregnancy test.

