3.5 SCHEDULE OF DATA COLLECTION

		Scre en	Baseline Visit	1 week visit	2 week visit	4 week visit	6 week visit	7 week visit	8 week visit	12 week visit
Screening	Screening Questions	Х								
3	Verification of HIV, non-pregnancy, urine tox, and ALT/AST	Х								
Enrollment	Sign Informed Consent	Х								
Linemient	Complete contact information/verify numbers	Х								
	Randomization		Х							
	Clinical Values		Х			X			Χ	X
Laboratory	Pregnancy Test	Х	Х	X	Х	Х	Х	X		
	Urine Drug Test	Х	Х							
	AST, ALT	X				х	X (if indicat ed)			
	Creatinine	Х								
	Cold Pressor Test		Х			Х			Х	Х
	Naloxone Challenge		Х							
	Blood Draw (IL-6, IL- 1β, IL-10, TNF-alpha, CD4, HVL)		Х						х	
Assessment	Full Study Assessment		Х			Х			х	Х
	Short Assessment			Х	Х		Х	Х		
Intervention	Symptom Management/Adverse Events		×	X	Х	Х	Х	X	×	X
	Provide Medication Instructions		Х		Х	Х	Х			
	Give Study Medication		Х		Х	Х	Х			
	Discuss Adherence		Χ	Χ	Х	Χ	Х	Х	Χ	
	Assess Adherence			Χ	Х	Х	X	Х	Х	
Other	Provide Resource Card		Х							
	Compensate for Participation	Х	Х	Х	Х	Х	Х	Х	Х	Х
	Report Adverse Events		Х	Х	Х	Х	Х	Х	Х	Х
	Complete Tracking Forms	Х	Х	Х	Х	Х	Х	X	Х	Х

3.5.A. VISIT WINDOWS

Baseline Visit

Window open: 1 day post screening

• Target date: 3 days post screening

• Window close: 28 days post screening

Window length: 27 days

1 Week Visit

• Window open: 5 days post baseline

Target date: 7 days post baseline

• Window close: 10 days post baseline

• Window length: 5 days

2 Week Visit

Window open: 11 days post baseline

• Target date: 14 days post baseline

• Window close: 20 days post baseline

Window length: 9 days

4 Week Visit

Window open: 21 days post baseline

• Target date: 28 days post baseline

Window close: 37 days post baseline

Window length: 16 days

6 Week Visit

Window open: 38 days post baseline

• Target date: 42 days post baseline

• Window close: 45 days post baseline

• Window length: 7 days

7 Week Visit

• Window open: 46 days post baseline

• Target date: 49 days post baseline

• Window close: 52 days post baseline

Window length: 6 days

8 Week Visit

• Window open: 53 days post baseline

• Target date: 56 days post baseline

Window close: 73 days post baseline

Window length: 20 days

12 Week Visit

Window open: 74 days post baseline
Target date: 84 days post baseline
Window close: 94 days post baseline

Window length: 20 days

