7.4 WEB SYSTEMS

The study will use REDCap. REDCap is a secure web application for building and managing online surveys and databases and will be used for screening and assessments purposes. Study forms will be completed according to the schedule below.

				STUDY VISIT							
FORM	Phon e Scre en	een & ine Visit Baselin e	1 week visit	2 week visit	4 week visit	6 week visit	7 week visit	8 week visit	12 week visit	As Needed	

Pre-Screener	X										
Screener		X									
Consent and enrollment form		X									
Full assessment			X			X			X	X	
Short assessment (adherence)				X	X		X	X			
Baseline Event Form			X								
Medication visit checklist			X	X	X	X	X	X	X		
Symptom Monitoring Form				X	X	X	X	X	X		
Naloxone Challenge Form			X								
Contact info		X	X	X	X	X	X	X	X	X	X
Contact log											X
Baseline tracking form			X								
Follow-up tracking form				X	X	X	X	X	X	X	
Lab forms		X	X		X	X	X		X		
Study conclusion form											X
AE/SAE form (paper and electronic form)											X
Medication collection (paper form)			X	X	X	X	X	X	X	X	

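### Sections conflict on whether the symptom checklist is given after study drug stops and at week 12

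*Combined protocol and SAP*

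**What the plan says.** The combined protocol and SAP points two ways.

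**On drug, or to week 8 only.**
- Section 6.3, before its 20-item list: "The following symptoms will be assessed at baseline and during medication check-ins and study visits while participant is taking the study medication". It adds: "All events will be documented on the Symptom Checklist and on AE forms".
- Section 3.4.A likewise ties symptom assessment to the period of study-drug administration.
- The 5.2.A table marks the "Follow-Up Symptom" Checklist row at weeks 1, 2, 4, 6, 7 and 8, and leaves week 12 blank.
- The 7.4 schedule marks the "Symptom Monitoring Form" at the same six visits. The AE/SAE form is listed as needed, not by visit.

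**Every visit.**
- Section 6.2: "During each scheduled visit, the RA will ask the participant how he or she feels and review the list of symptoms of concern". It sets no on-drug condition.
- The 3.5 schedule marks "Symptom Management/Adverse Events", and a separate row for reporting adverse events, from baseline to week 12.

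Three other passages bear on which was meant. Section 6.1 defines an adverse event over the course of the study. Section 6.3.C extends SAE reporting to the follow-up phase. On early stopping, section 3.4.E says: "Those who discontinue medication will be followed and analyzed by intention to treat".

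**The concern.** A checklist finds more symptoms than an open question does, so the arms can be compared fairly only if it is given on the same schedule in each. Two things could go wrong.

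First, the protocol adds four weeks of observation after treatment, yet the forms schedule no checklist there. Section 6.2 asks for the list to be reviewed at week 12, but no symptom form is scheduled at that visit to hold the answers.

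Second, if the list is asked only of people still taking drug, its use depends on stopping, which is itself a tolerability outcome. An arm with more early stopping would then have fewer occasions on which symptoms are prompted. Section 8 contains no adverse-event analysis, counting window or exposure adjustment, so any such shortfall would pass straight into counts by arm. Tolerability has mattered in this programme: section 1.1 says nalmefene was replaced because it was not tolerable.

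**Working it through.** The plan states no figure on this point, so there is none to reproduce. The check is to count checklist cover under each reading.

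**Inputs.** Post-baseline visits are at weeks 1, 2, 4, 6, 7, 8 and 12, seven in all (section 3.1). Treatment lasts 8 weeks, with 4 weeks of post-treatment observation (section 2.3). Stopping rates by arm are not given. Section 2.7.A gives only overall dropout, under 15% by week 8. The stopping rates below are therefore assumptions.

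**Table alignment.** In 7.4 the follow-up tracking row starts at the same visit as the symptom form and has seven marks; the symptom form has six. The missing one is week 12.

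**Cover for one participant** (visits of 7; weeks of 12 up to the last checklist, counting the checklist at the stopping visit as given):

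| Drug stopped | 6.3 literal | 5.2.A and 7.4 | 6.2 and 3.5 |
|---|---|---|---|
| Week 8 (completer) | 6 visits, 8 weeks | 6 visits, 8 weeks | 7 visits, 12 weeks |
| Week 4 | 3 visits, 4 weeks | 6 visits, 8 weeks | 7 visits, 12 weeks |
| Week 2 | 2 visits, 2 weeks | 6 visits, 8 weeks | 7 visits, 12 weeks |

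**Week-12 gap.** At target dates, 84 − 56 = 28 days, and 28/84 = 33% of follow-up. It is the same for every arm.

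**Arm comparison under 6.3 read literally.** If a fraction d of an arm stops at week s and the rest complete, mean covered weeks are W = (1 − d) × 8 + d × s, and the ratio to an arm with no stopping is W/8.
- d = 0.20, s = 4: 6.4 + 0.8 = 7.2; ratio 0.90.
- d = 0.40, s = 4: 4.8 + 1.6 = 6.4; ratio 0.80.
- d = 0.40, s = 2: 4.8 + 0.8 = 5.6; ratio 0.70.

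Under 5.2.A and 7.4, or under 6.2 and 3.5, the ratio is 1.00 for any d, because those schedules go by week and not by drug status.

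**Sensitivity to week 8.** Section 3.3 dispenses 14 + 7 + 14 + 14 + 7 = 56 days of drug, starting on the baseline day (day 0). The last capsule falls on day 55 and an on-target week-8 visit on day 56. Strictly, then, a completer is already off drug at week 8. Replacing 8 by 7 for completers, d = 0.20 and s = 4 gives 5.6 + 0.8 = 6.4 against 7.0; ratio 0.91. In checklists for 15 per arm with 3 stopping at week 4, the comparison is 81 against 90 (0.90) if week 8 counts, and 69 against 75 (0.92) if it does not.

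**The case against.** The strongest reply is that this is a mismatch about one form, not a hole in safety surveillance. Much of that stands.

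A reader might infer that harms after stopping are not elicited, or are left to spontaneous report. The documents do not support this. Section 6.2 requires active asking at every scheduled visit, 3.5 marks it at week 12, and events discovered between visits must be recorded. The GAD-7 and CES-D are also scheduled at week 12 (5.2.A), so anxiety and depressive symptoms are measured there.

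A reader might also infer that resolution of the event that led to stopping goes unrecorded. It does not: 6.3.B follows all adverse events to resolution, stabilisation or end of participation, 6.4 repeats this for non-mild events, and 6.2 starts each review from the symptoms noted at the previous visit.

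Nor do the form tables take the checklist away from early stoppers. They schedule it by week through week 8, and 3.4.E keeps those participants in follow-up. The 5.2.A columns are headed by treatment and post-treatment phase, so the wording in 6.3 can fairly be read as meaning the treatment phase. On that reading no arm imbalance arises.

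Finally, section 3.3.B says of gabapentin participants in week 8: "when they will be tapered back down to 900 mg daily". A reader might take this to show that the plan treats stopping as an exposure in its own right. The section gives no reason for the step, so nothing here rests on it.

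What survives is that the sections disagree, that both form schedules leave week 12 blank, and that 6.3 and 3.4.A can be read as ending the list when drug ends.

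**Conclusion.** The inconsistency is real and should be reconciled. Its certain part is small and equal across arms: on the form schedules, no structured checklist is given in the post-treatment period, 28 of 84 days at target dates.

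The part that differs between arms is conditional. It needs staff to follow 6.3 literally and early stopping to be unequal. Under assumed stopping of 20% to 40% in one arm and none in the other, covered time falls to between 0.90 and 0.70 of the comparison arm's, or 0.91 in place of 0.90 if week 8 is also treated as off drug. If the 5.2.A table governs, there is no difference. The documents do not establish that any arm will be under-ascertained. They leave it possible because they do not say which passage governs.

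**What to change.** 1. In section 6.3, replace the on-drug condition with: *at every attended visit through week 12, whether or not study medication has been stopped*. Align section 3.4.A.
2. Add the week-12 mark to the Follow-Up Symptom Checklist row in 5.2.A and to the Symptom Monitoring Form row in 7.4, to match 6.2 and 3.5.
3. Record the date of last dose for every participant, and add to section 8 a tabulation of adverse events by arm, split into on drug and after last dose.

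The cost is wording in two sections, one mark in each of two tables, a date field if the forms do not already hold one, and a short table in the analysis. Participants answer the existing 20-item list once more at a visit already held, which takes a few minutes. Early stoppers answer it at visits they already attend.
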